#### *Step 1 – Power analysis for severe hypoglycemia (SH)*

An overall incidence rate of 25.35 events per 100 patient years (PY) was used in the power analysis for severe hypoglycemia. We calculated that a sample size of 1,354 individuals with T1D would provide 80% power with a type 1 error rate (two-sided) of 5% to detect a difference, if there is one, between the expected SH rate (25.35) and the proposed study sample SH event rate.

A separate power analysis for the 14-18 age group used an overall SH incidence rate of 19.5 events/100PY. Results indicated that a sample size of 231 individuals with T1D between the ages of 14-18 would provide 80% power with a type 1 error rate (two-sided) of 5% to detect a difference, if there is one, between the expected SH rate (19.5) and the proposed study sample SH event rate. Of the overall sample of 1,354 subjects, at least 231 subjects will be 14-18 years old to provide sufficient power to detect risk of SH in this younger age group.

A separate power analysis for the 6-13 year old group used a SH incidence rate of 21.9 events/100PY, which is a weighted average of both MDI and pump users (since pump users were overrepresented in this age group). Results indicated that a sample size of 288 individuals with T1D between the ages of 6 and 13 would provide 80% power with a type 1 error rate (two-sided) of 5% to detect a difference, if there is one, between the expected SH rate (21.9) and the proposed study sample SH event rate. In addition to

the overall sample, at least 288 subjects will be 6-13 years old to provide sufficient power to detect risk of SH in this younger age group. *Step 2 – Power analysis for diabetic ketoacidosis (DKA)*

An overall incidence rate of 11.03 events per 100 patient years was used in the power analysis for DKA . We calculated that a sample size of 1,282 individuals with T1D would provide 80% power with a type 1 error rate (two-sided) of 5% to detect a difference, if there is one, between the expected DKA rate (11.03/100 PY) and the proposed study sample DKA event rate.

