A separate power analysis for the 14-18 age group used an overall DKA incidence rate of 14.2 events/100PY. Results indicated that a sample size of 328 individuals with T1D between the ages of 14-18 would provide 80% power with a type 1 error rate (two-sided) of 5% to detect a difference, if there is one, between the expected DKA rate (14.2) and the proposed study sample DKA event rate. Of the overall sample of 1,282 subjects, at least 328 subjects will be 14-18 years old to provide sufficient power to detect risk of DKA in this younger age group.

A separate power analysis for the 6-13 year old group used an overall DKA incidence rate of 13.2 events/100PY, which is a weighted average of both MDI and pump users (since pump users were overrepresented in this age group). Results indicated that a sample size of 77 individuals with T1D between the ages of 6-13 would provide 80% power with a type 1 error rate (two-sided) of 5% to detect a difference, if there is one, between the expected DKA rate (13.2/100PY) and the proposed study sample DKA event rate. In addition to the previously determined sample, at least 77 subjects will be 6-13 years old to provide sufficient power to detect risk of DKA in this younger age group.

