### ***Step 3 – Final sample size determination***

The projected total recruitment sample size of at least 2,063 subjects (including attrition) would provide 80% power with a 2-sided type 1 error rate of 5%. Considering the 25% attrition mentioned above, it is the expectation to have 1,354 subjects complete the study. Recruitment goals for study subgroups will include:

- At least 385 subjects in the 6 to 13 year old cohort, and at least 328 subjects in the 14 to  $\leq$  18 year old cohort. Depending on the rate of recruitment in these two age groups, the balance of the total sample will be recruited from the  $>18$  year old subgroup.
- Of the 6-13 year old cohort:
  - At least (n=163) will be 6-9 years old, as recently published data of 30 children age 6-9 shows successful use of Control-IQ technology (10).
  - At least 25% (n=96) will have a baseline A1c  $\geq$  8.5%
  - At least 25% (n=96) will be pump naïve
  - At least 5% (n=18) will be CGM naïve. This percentage is based on clinical evidence of high baseline CGM use in this age group, and recently published data of 40 CGM naïve children who successfully used Control-IQ

technology (10). With the availability of this data from these 40 participants, recruitment goals for the CGM naïve cohort of children in CLIO was reduced to 18 participants.

- Of the >14 year old cohort,
  - Approximately 677 subjects each in the pump user and pump naïve subgroups at baseline.
  - Approximately 270 subjects that are CGM naïve (defined as not using CGM in the 30 days prior to enrollment).
  - Approximately 681 subjects (33% of total sample) with HbA1c  $\geq 8.5\%$  and 681 subjects (33% of total sample) in the <8.5% subgroup

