## **Primary Outcome**

Incidence rate/100 patient years for both severe hypoglycemia (SH) and diabetic ketoacidosis (DKA).

**Success Criteria/Goal:** Study participants will not experience a higher incidence of SH or DKA than incidence rates reported in the literature from analyses of similar populations. Overall outcomes will be compared to data below, derived from a recently published study using a large Type 1 Diabetes Exchange cohort (Foster et al., 2019). This study used a similar design as our postmarket study proposed here, the subjects represent our intended use population, and the event rates reported in the Foster study fall within the broader rates found in the extensive body of literature reviewed.

SH Incidence Rates (all ages)		SH Incidence Rates in Children			SH Incidence Rates in Adults	
All ages (13-93)			Ages 6-12	Ages 13-17	Ages 18-93	
All insulin delivery	25/100 PY	All insulin delivery	22/100 PY	20/100 PY	All insulin delivery	30/100 PY
MDI	37/100 PY	MDI	28/100 PY	34/100 PY	MDI	38/100 PY
IPT	23/100 PY	IPT	16/100 PY	13/100 PY	IPT	27/100 PY
DKA Incidence Rates (all ages)		DKA Incidence Rates in Children			DKA Incidence Rates in Adults	
All ages (13-93)			Ages 6-12	Ages 13-17	Ages 18-93	
All insulin delivery	11/100 PY	All insulin delivery	13/100 PY	14/100 PY	All insulin delivery	9/100 PY
MDI	17/100 PY	MDI	22/100 PY	25/100 PY	MDI	13/100 PY
IPT	7/100 PY	IPT	5/100 PY	9/100 PY	IPT	7/100 PY

The full literature review can be found in Attachment 1 of this protocol.

The safety of automatically populating CGM readings into the bolus calculator will be analyzed by correlating reported AEs, calculator usage data and CGM readings to understand if the bolus calculator may have caused the AE. This analysis will isolate AEs where three consecutive CGM readings  $\leq 54$  mg/dL, or  $\geq 250$  mg/dL existed within five hours of receiving a correction bolus using an automatically populated CGM reading. All CGM readings within 5 hours after the bolus is given will be evaluated. In addition, correction boluses using automatically populated CGM values  $\geq 250$  mg/dL will be analyzed and evaluated separately from boluses given for lower glucose values.

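### The 6-13 reference rates imply about half injection users, but the quota guarantees only 25% pump-naive children and nothing adjusts the comparison to the enrolled mix; at that floor the DKA reference would be about 43% too high

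*Combined protocol and SAP*

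**What the plan says.** Under Determination of Sample Size, Step 1 sets the 6-13 severe hypoglycemia (SH) reference at "21.9 events/100PY, which is a weighted average of both MDI and pump users". Step 2 sets the DKA reference at "13.2 events/100PY, which is a weighted average of both MDI and pump users (since pump users were overrepresented in this age group". Neither step gives the weights.

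The table under Primary Outcome splits the rates by delivery method. For ages 6-12 (first figure in each row) the DKA rows read "MDI 22/100 PY 25/100 PY" and "IPT 5/100 PY 9/100 PY". The SH row for injections reads "MDI 28/100 PY 34/100 PY", and the pump figure is 16. The all-delivery rows for ages 6-12 show 22 (SH) and 13 (DKA), which are 21.9 and 13.2 rounded.

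Step 3 states the prior-therapy goal for the 6-13 cohort of at least 385 children: "At least 25% (n=96) will be pump naïve". It gives no upper limit and no target for equal groups. For the cohort over 14, by contrast, it plans about 677 pump users and about 677 pump-naive subjects.

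The Statistical Analysis section compares observed rates with literature values by a one-sample two-tailed exact binomial test at alpha 0.05. It describes no adjustment for prior therapy. The goal under Primary Outcome is: "Study participants will not experience a higher incidence of SH or DKA than incidence rates reported in the literature from analyses of similar populations".

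**The concern.** The sponsor reweighted the children's rates because it regarded the pump/injection mix as material to the expected rate. The recruitment rule then permits a mix far from the one the reweighting implies. In the plan's table, DKA in this age group is more than four times as frequent on MDI as on pumps (22 against 5), so the reference depends heavily on the mix. Existing t:slim X2 owners are eligible through a software update (Initiation of therapy section), so a cohort made up mostly of pump users is possible.

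If the enrolled children are mainly pump users, a reference that is half MDI is not a rate from a similar population. The error then runs in the unsafe direction: a real rise in DKA among the youngest users could look like no rise, and a device with no effect could look protective.

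**Working it through.** **Inputs.** Ages 6-12 rates per 100 PY, from the Primary Outcome table: DKA 22 (MDI) and 5 (pump); SH 28 and 16. References from Steps 1 and 2: 21.9 and 13.2. Quota floor 25% and cohort size 385, from Step 3. Attrition 25%, so 385 × 0.75 = 288.75, taken as 289 children with one year each.

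**Reproducing the references.** Reference = w × MDI + (1 − w) × pump.
- w = 0.5 gives DKA 13.5 (stated 13.2) and SH 22.0 (stated 21.9).
- Solving for w: DKA (13.2 − 5)/(22 − 5) = 0.48; SH (21.9 − 16)/(28 − 16) = 0.49.
- Letting each table rate vary by ±0.5 gives 0.45-0.51 (DKA) and 0.45-0.53 (SH).

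Both endpoints point to a mix close to half and half.

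**Expected rate at the quota floor.**
- DKA: 0.25 × 22 + 0.75 × 5 = 9.25. 13.2/9.25 = 1.43, a 43% excess (35-51% over table rounding). Using the table's 13: 13/9.25 = 1.41.
- SH: 0.25 × 28 + 0.75 × 16 = 19.0. 21.9/19.0 = 1.15, a 15% excess (12-18%).

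**Other permitted mixes (DKA).**

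| Pump-naive share | Expected DKA per 100 PY | 13.2 relative to expected |
|---|---|---|
| 25% | 9.25 | +43% |
| 30% | 10.10 | +31% |
| 35% | 10.95 | +21% |
| 40% | 11.80 | +12% |
| 45% | 12.65 | +4% |
| 50% | 13.50 | −2% |

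**Effect on the test.** Exact binomial, n = 289, two-sided 5%, treating the rate as a one-year proportion as the planned test does. Against 13.2, rejection is at 26 or fewer events or at 50 or more. Against 9.25, the upper limit is 37; against 10.95, it is 43. No effect means that the true rate equals the mix-matched expectation. The 1.6-fold excess is 1.6 × 9.25 = 14.8 at a 25% share and 1.6 × 10.95 = 17.5 at a 35% share.

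| | 25% pump-naive | 35% pump-naive |
|---|---|---|
| No effect, called significantly lower than 13.2 | 49% | 17% |
| 1.6-fold excess detected against 13.2 | 13% | 56% |
| 1.6-fold excess detected against matched rate | 85% | 90% |

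The plan does not state the two-sided convention. These figures use the minimum-likelihood p-value. With equal tails the upper limits become 51 (against 13.2) and 38 (against 9.25), and the 13% and 85% become 10% and 81%; the pattern is unchanged.

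**Pooled comparison, same method.** Take 385 children at the floor and the other 2,063 − 385 = 1,678 subjects at half and half on the all-ages rates (DKA 17 and 7, mean 12; SH 37 and 23, mean 30).
- DKA: (385 × 9.25 + 1,678 × 12)/2,063 = 11.5, against a planning rate of 11.03.
- SH: (385 × 19.0 + 1,678 × 30)/2,063 = 27.9, against 25.35.

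On these assumptions the pooled references are slightly too low, not too high.

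**The case against.** Several counter-arguments have force.

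- **The quota is a floor.** Nothing in the documents shows that enrolment will sit at 25%, and the distortion falls quickly as the share rises. This stands: 43% is the worst permitted case, not a forecast.
- **The rates 21.9 and 13.2 are power-analysis inputs.** The Primary Outcome section speaks of comparing overall outcomes, and no separate decision rule for ages 6-13 is written. This stands in part. The same rates reappear, rounded, as the ages 6-12 all-delivery figures beneath the success goal, and the cohort was sized separately for these two endpoints. A subgroup comparison is therefore clearly intended, although the plan does not say which row applies.
- **Benchmarking to general type 1 care is legitimate.** The protocol says that the reviewed literature represents the typical population, and every child uses a pump during follow-up. On that view the reference need not follow each child's prior therapy. The choice is defensible, but the goal refers to similar populations and the plan does not say which mix it regards as similar.
- **Mapping prior therapy to a rate is an assumption.** Baseline pump users may also include users of predictive suspension, whom the plan excludes from the comparator. This stands, and is a reason to report the matched comparison beside the fixed one and not in its place.
- **The plan has the ingredients already.** The MDI and pump rates are tabulated, prior therapy is collected, and a detailed SAP is promised. That makes the repair easy, but does not supply it.

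A reader might infer that the study's overall safety criterion is biased towards success. The pooled calculation does not support that. A reader might also extend the point to ages 14-18 by setting those reference rates against the half-and-half pump goal. The documents do not support that either: the 677/677 goal covers everyone over 14, adults included, and no pump-naive quota exists for ages 14-18.

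**Conclusion.** The concern holds for the 6-13 subgroup and should be fixed. The reference rates for children imply 48-49% MDI users, recruitment guarantees only 25% pump-naive, and nothing links the two. At the floor the DKA reference would be about 43% too high and the SH reference about 15%; at 35% pump-naive the DKA figure is 21%. Above about 48% the error reverses. At or near the floor, the loss of power to see a DKA excess is large enough to change the safety conclusion for this cohort.

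This rests on four assumptions: pump-naive children carry the MDI rate and all others the pump rate; the ages 6-12 rates apply to ages 6-13; the rounded table rates are close to the source values; and 289 children contribute one year each. The source weights may be given in Attachment 1, which was not available for this check.

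**What to change.** In Statistical Analysis and Primary Outcome, add for the 6-13 cohort a comparison of observed events with an expected count:

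- DKA: patient-years of pump-naive children × 22/100 + patient-years of pump-experienced children × 5/100.
- SH: the same with 28/100 and 16/100.

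Report it beside the fixed-rate comparison, and state the assumption that links prior therapy to the expected rate. In Steps 1 and 2, state the therapy mix that 21.9 and 13.2 assume, and give the rates at the 25% floor (19.0 and 9.25).

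The cost is wording only. Previous therapy is already collected at baseline (Medical History) and the rates by delivery method are already tabulated. Because the count follows the mix actually enrolled, it corrects the error in either direction. The drawbacks are that the reference for children may become less favourable to the device, and that it depends on the stated mapping of prior therapy to rate.

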### ***Step 3 – Final sample size determination***

The projected total recruitment sample size of at least 2,063 subjects (including attrition) would provide 80% power with a 2-sided type 1 error rate of 5%. Considering the 25% attrition mentioned above, it is the expectation to have 1,354 subjects complete the study. Recruitment goals for study subgroups will include:

- At least 385 subjects in the 6 to 13 year old cohort, and at least 328 subjects in the 14 to  $\leq$  18 year old cohort. Depending on the rate of recruitment in these two age groups, the balance of the total sample will be recruited from the  $>18$  year old subgroup.
- Of the 6-13 year old cohort:
  - At least (n=163) will be 6-9 years old, as recently published data of 30 children age 6-9 shows successful use of Control-IQ technology (10).
  - At least 25% (n=96) will have a baseline A1c  $\geq$  8.5%
  - At least 25% (n=96) will be pump naïve
  - At least 5% (n=18) will be CGM naïve. This percentage is based on clinical evidence of high baseline CGM use in this age group, and recently published data of 40 CGM naïve children who successfully used Control-IQ

technology (10). With the availability of this data from these 40 participants, recruitment goals for the CGM naïve cohort of children in CLIO was reduced to 18 participants.

- Of the >14 year old cohort,
  - Approximately 677 subjects each in the pump user and pump naïve subgroups at baseline.
  - Approximately 270 subjects that are CGM naïve (defined as not using CGM in the 30 days prior to enrollment).
  - Approximately 681 subjects (33% of total sample) with HbA1c  $\geq 8.5\%$  and 681 subjects (33% of total sample) in the <8.5% subgroup

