Study Population	Enrollment in the study will be available to all subjects who start therapy with the Control-IQ System once the Institutional Review Board (IRB) approval is received and the subject meets the indications for use and the study eligibility criteria. As specific target subgroups are filled, we may elect to only

	enroll subjects whose subgroup recruitment goals have not been completed. Electronic informed consent will be required from all subjects prior to participation in the study.
Number of Subjects	
The study will recruit a minimum of 2,063 subjects. For the primary safety endpoints, the projected total recruitment sample size of at least 2,063 subjects (including 25% attrition) would provide 80% power with a 2-sided type 1 error rate of 5%. With attrition, it is expected that 1,547 subjects will complete the study. Recruitment goals for study subgroups will include:
 
 
• At least 385 subjects in the 6 to 13 year-old cohort, and at least 328 subjects in the 14 to <math>\leq</math>18 year-old cohort. Depending on the rate of recruitment in these two age groups, the balance of the total sample will be recruited from the <math>></math>18 year-old subgroup.
 
• Details on subgroup enrollment targets can be found on page 23 “Determination of Sample Size”
 

Number and Location of Sites	All data for this study will be collected remotely, with no live clinical visits conducted. Data will be collected electronically, via surveys and automated uploads of pump and CGM data, as well as via in- and out-bound telephone calls and SMS messaging.

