### **Study Design**

This post-approval study is a single-arm, prospective, longitudinal study. It is designed to assess the 12-month safety and effectiveness of this FDA approved product in a post-approval setting, and to support the continued assessment of the t:slim X2 insulin pump with Control-IQ technology for the treatment of type 1 diabetes in the US. In addition, data will be collected to assess the experience of patients using the Control-IQ system.

This study will enroll a minimum of 1698 subjects over a two-year period. All enrolled subjects will be monitored from baseline through 12 months following the initiation of therapy with the Control-IQ System.

The data collected in this study will be entered into either Qualtrics, a HIPAA compliant software database, or an electronic data capture system (EDC) using electronic case report forms (eCRFs). Subject data will include participant reported demographics, medical history, and baseline therapy information along with therapy data, and follow-up measures.

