## SUBJECT SELECTION

### Subject Population

**Inclusion Criteria:** Patients must consent to meet the following criteria in order to be enrolled in the study:

- 1) Patients with self-reported type 1 diabetes who have been prescribed the Control-IQ system.
- 2) At least 6 years of age
- 3) Using Humalog or Novolog insulin
- 4) For females, not pregnant or planning pregnancy in the next 12 months.
- 5) Agreement to use the t:slim X2 with Control-IQ technology, and to continue use for at least 12 consecutive months after study enrollment.
- 6) Agree to provide HbA1c result, obtained within the 6-month period prior to enrollment.
- 7) Ability to respond to alerts and alarms, and to provide basic diabetes self-management.
- 8) Patients who reside full-time in the United States.
- 9) Willingness to download the t:connect Mobile application to their Smartphone and keep it active throughout the study. Patients unable to use t:connect mobile application must be willing to manually upload their insulin pump data to t:connect every three months and at the completion of the study.
- 10) Subject has read, understood and agreed to participate in the study, and has electronically signed the Informed Consent Form (ICF).

**Exclusion Criteria:** Patients with the following characteristics will not be considered candidates for the study:

- 1) Self-reported type 2 diabetes
- 2) < 6 years of age
- 3) Use of any glucose-lowering therapy other than Humalog or Novolog insulin
- 4) Inability to respond to alerts and alarms, or to provide basic diabetes self-management.
- 5) Pregnancy
- 6) Subjects who have not signed the ICF.

Any discrepancy in the above criteria between data in CRM and subject's self-reported criteria will be electronically alerted to study staff. Study staff will then clarify inclusion/exclusion criteria prior to enrolling the subject.

Over the course of the study as specific participant recruitment subgroups are filled, we may enroll subjects whose subgroup goals have not been completed and elect to exclude otherwise applicable participants.

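### Minimum enrolment (1,698 or 2,063) and expected completers (1,354 or 1,547) each have two values in the current protocol, and the 14-18 DKA power and the basis of the overall power need restating

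*Combined protocol and SAP*

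**What the plan says.** **Minimum enrolment.** The synopsis (Number of Subjects) says: "The study will recruit a minimum of 2,063 subjects". Step 3 of Determination of Sample Size also gives at least 2,063, including attrition. The Study Design section says: "This study will enroll a minimum of 1698 subjects over a two-year period".

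**Expected completers.** The synopsis applies 25% attrition to 2,063: "With attrition, it is expected that 1,547 subjects will complete the study". Step 3 starts from the same 2,063: "Considering the 25% attrition mentioned above, it is the expectation to have 1,354 subjects complete the study". Steps 1 and 2 never mention the 25%; it is stated only in the synopsis.

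**Age floors.** Step 3 sets recruitment goals of "At least 385 subjects in the 6 to 13 year old cohort, and at least 328 subjects in the 14 to" 18 years. The DKA power analysis for ages 14-18 reads: "Results indicated that a sample size of 328 individuals with T1D between the ages of 14-18 would provide 80% power". For ages 6-13 the larger of the two required Ns is 288 (SH).

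**Overall sample.** The required Ns are 1,354 for SH (reference rate 25.35 per 100 patient-years, PY) and 1,282 for DKA (11.03 per 100 PY). Steps 1 and 2 take the 14-18 group from within the overall sample but describe the 6-13 group as additional to it. The Primary Outcome table labels its all-ages reference rates as covering ages 13 to 93. Step 3 counts the 6-13 cohort inside the 2,063.

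**The concern.** A study has one enrolment minimum, and one recruitment total at one attrition rate gives one completer count. Here each has two values in current text, and these are the figures the study is run and reported against. A team working to the Study Design section could stop 365 subjects short of the synopsis (2,063 - 1,698). A reader of Step 3 could take a one-third loss as planned.

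Two further gaps affect the power statements, at lower priority:

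- If 328 adolescents are needed for 80% DKA power and only 328 need be recruited, attrition erodes that power. The Subject Population section allows enrolment to close by subgroup: "we may enroll subjects whose subgroup goals have not been completed and elect to exclude otherwise applicable participants".
- If children are additional to the 1,354, as Step 1 says, then 2,063 recruits do not yield enough completers for both groups. If children are included, they do. Step 3 claims 80% without saying which.

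**Working it through.** **1. Completers.** Inputs: 2,063 recruits and 25% attrition (synopsis).
- 2,063 x (1 - 0.25) = 1,547.25, so the synopsis figure of 1,547 reproduces.
- Step 3's 1,354 does not: 1 - 1,354/2,063 = 34.4% attrition. The gap is 1,547 - 1,354 = 193.
- 1,354 is the overall SH power N in Step 1.

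**2. Enrolment minimum.** Step 3 contains its own check: "Approximately 681 subjects (33% of total sample) with HbA1c" at or above 8.5%.
- 681/2,063 = 33.0%; 681/1,698 = 40.1%. Only 2,063 fits.
- 1,698 x 0.75 = 1,273.5, below both 1,354 and 1,282.

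**3. Attrition in the age floors.**
- Ages 6-13: 288/0.75 = 384, against a floor of 385. This is consistent with an attrition allowance, though the plan does not say so.
- Ages 14-18: 328 x 0.75 = 246 completers. If dropouts contribute half a year on average (assumption), 246 + 82 x 0.5 = 287 PY.

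**4. Overall sample if children are additional.**
- Completers needed: 1,354 + 288 = 1,642. Completers expected: 1,547. Shortfall: 95. With no credit for dropouts, 1,642/0.75 = 2,189.3, so 2,190 recruits would be needed.
- With 385 children enrolled, ages 14 and over number 2,063 - 385 = 1,678, giving 1,678 x 0.75 = 1,258 completers. Half-year credit gives 1,678 x 0.875 = 1,468 PY.

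**5. Power.** The plan states no alternative rates, so its 80% figures cannot be reproduced directly. Each stated N was assumed to give exactly 80% at two-sided 5%, the alternative was solved for, and power was recomputed at the reduced N. The test is the plan's exact binomial, treating PY as n (assumption). Ranges cover both directions of effect and two versions of the two-sided test (doubled tail, minimum likelihood).

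Alternatives obtained, per 100 PY: SH 22.1 or 28.7-28.8 against 25.35; DKA 8.7 or 13.6 against 11.03; 14-18 DKA 9.2 or 20.0 against 14.2.

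| Situation | n | Power |
|---|---|---|
| 1,698 enrolled, all ages, completers only | 1,273 | SH 77-79%, DKA 80% |
| 1,698 enrolled, half-year credit (1,698 x 0.875) | 1,485 | SH 83-84%, DKA 84-86% |
| 2,063 enrolled, all ages, completers only | 1,547 | SH 84-86%, DKA 86-88% |
| 2,063 enrolled, ages 14+, completers only | 1,258 | SH 76-78%, DKA 78-80% |
| 2,063 enrolled, ages 14+, half-year credit | 1,468 | SH 82-84%, DKA 83-85% |
| 14-18 DKA at the floor, completers only | 246 | 66-67% |
| 14-18 DKA at the floor, half-year credit | 287 | 68-76% |

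Taking instead the Primary Outcome table's pump-therapy DKA rate for ages 13-17 (9 per 100 PY) as an assumed alternative, 14-18 power is 83% at 328, 71% at 246 and 72-78% at 287.

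Exact-test power moves in steps as n changes. At 245 completers the same method gives 60-71%, so the 66-67% at 246 should be read as roughly two-thirds.

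**The case against.** The two contradictions are not in dispute. The case against concerns their weight and the two lesser points.

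- **The intended minimum is clear.** The synopsis and Step 3 agree on 2,063, the revision history calls it the original intention, and nothing in the plan proposes stopping at 1,698. This shows which number to keep, but the Study Design sentence is still wrong.
- **1,354 may be a leftover count for the older cohort.** Step 3's pump-user and pump-naïve goals for that cohort are 677 each, and 677 + 677 = 1,354. This may explain where the number came from. It does not rescue a sentence that presents 1,354 as what remains of 2,063 after 25% attrition, when the synopsis already gives 1,547 for that calculation.
- **The 14-18 shortfall is conditional.** The floor is a minimum, closing at it is optional, the success criterion is overall with no separate 14-18 rule, and the power figures rest on assumed alternatives. All of this stands and keeps the point at lower priority.
- **The overall 80% is not shown to be false.** With children included, power exceeds 80%. For ages 14 and over it does so with half-year credit. Only ages 14 and over with no dropout credit falls short, by at most about four points. Subject Withdrawal or Termination keeps withdrawn subjects' data in the analysis, so zero credit is the pessimistic reading. This stands; the request is for the basis to be stated.

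**Conclusion.** The concern holds. Two points are certain and need no assumption: minimum enrolment is stated as both 1,698 and 2,063, and expected completers as both 1,354 and 1,547, a difference of 193. The plan's own arithmetic supports 2,063 and 1,547.

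The other two points are conditional. If 14-18 enrolment stops at 328, DKA power falls from the stated 80% to roughly two-thirds on completers, or 68-76% if dropouts contribute half a year. If the 6-13 cohort is additional to the overall sample, overall power is about 76-80% on completers and 82-85% with half-year credit; if children are included it is about 84-88%. These figures rest on back-solved alternatives, on PY treated as binomial n, and on the assumed follow-up of dropouts. This should be fixed: the errors are in headline sample size figures and cost almost nothing to correct.

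**What to change.** 1. In Study Design, replace 1,698 with 2,063.
2. In Step 3, replace 1,354 expected completers with 1,547, and state the 25% attrition there rather than referring back to text that does not contain it.
3. In Step 3, restate the 14-18 DKA power at the floor of 328, giving the alternative rate and the follow-up credited to dropouts.
4. In Step 3, say whether the overall test at 2,063 includes the 6-13 cohort, and give the overall power and follow-up assumption on that basis.

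The cost is two number corrections and about two restated power sentences, with no change to enrolment.

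Optionally, the 14-18 floor could rise to 438 (328/0.75 = 437.3), or 375 with half-year credit (328/0.875 = 374.9), within the unchanged 2,063. That would move 110 or 47 places from adults to adolescents. The documents do not show that those adolescents can be recruited, so this is not requested.
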